OLO is hypothesized to allow shorter time to CBC results, by minimizing the time period from phlebotomy to results, currently prolonged due to the need to send blood samples from the oncology

daily care center to the central lab. By that, Sight OLO would improve workflow efficiency and provide care to patients in a reliable and accelerated fashion.

Study Description

Provide a concise overview stating the type of study, phase, design, and compounds

Study design:

This evaluation will include two studies:

1. A matrix study will compare a capillary sample collected via finger prick with a venous sample collected into a blood tube, both scanned on OLO.
2. A method comparison study will compare Sight OLO to Beckman Coulter DxH800 using a venous sample collected into a blood tube.

During a period of 2 weeks, approximately 50 whole blood samples will be collected from patients at the oncology daily care center.

Patient Enrollment:

- Each patient participating in the study will firstly fill and sign an Informed Consent Form (ICF). Subjects participating in the study will be rewarded with a coupon for coffee and cake.
- For de-identification purposes, study barcode stickers will be used for all of OLO scans, instead of the original patient identification details. An unblinded form will be used to match the de-identification barcode with the patient identification details (this form will remain at the center and will not be shared externally).
- Patient enrollment will be documented in a designated worksheet, using the study barcode stickers.
- The patient will be asked to rest for at least 15 minutes.

Phlebotomy and Scanning Flow:

During the routine blood collection, an additional venous sample will be collected in K₃EDTA tube as part of the study. The phlebotomy time will be recorded in the worksheet.

The first tube will get a study barcode sticker and remain in the daily care center at a room temperature of 18°C-26°C. The second tube will be sent to the lab to be scanned on Beckman Coulter DxH800, as part of the routine procedure.

Two consecutive finger prick samples will be collected from the 3rd and 4th fingers of the patient's non-dominant hand (in this order) and scanned on OLO, and the time of the first result will be recorded in the study worksheet.

Following two successful finger prick scans, the venous sample (collected previously for the study) will be scanned on OLO.

The following time points will be recorded in the study worksheet:

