- Phlebotomy time
- Scanning time on the reference device at the lab.

This study design is illustrated in the study scheme below.

Study Requirements:

- All four scans will be performed within no more than 2 hours.
- All scans should be performed within 8 hours from phlebotomy.
- Venous samples should be collected in K₃EDTA tubes with a minimum volume of 700µL and kept at room temperature of 18°C-26°C throughout the day until the last scan is completed.
- The finger prick samples will be collected using lancets provided by Sight.
- If a finger prick scan is rejected, another sample will be collected from another finger, in the following order: non-dominant 3rd -> non-dominant 4th -> dominant 3rd -> dominant 4th. Up to 4 finger prick attempts will be performed **in total** for the two finger prick scans. If less than 2 finger prick scans are completed successfully, the sample should be excluded from the study. For each successful scan, the corresponding finger will be recorded in the worksheets.
- In case any of the venous scans are rejected, an additional repeat should be performed. Up to 3 attempts will be performed for each sample, and in case a 3rd failure occurs, the sample should be excluded from the study.
- Only 1 reference device should be used throughout this study - Beckman Coulter DxH800.
- A single operator will participate in the study.
- All relevant documents, including forms, worksheet and barcode stickers will be provided by Sight.

Primary endpoint:

Following the initial period of 2 weeks in which the samples will be randomly selected, the results will be evaluated to assess the coverage of the predefined range groups (specified in the study population section), in order to understand the timeframe and the type and quantity of samples required for completion of the study. If needed, a purposeful method for samples collection will be used, according to the missing ranges.

Purposeful Sampling Method - Study Design: A sample will be enrolled according to the result received from the routine CBC test from the same day (on Beckman Coulter DxH800) and incomplete range groups (specified in table 1). Once enrolled in the study, the samples collection and scanning will be performed in the same order as in the initial phase (illustrated in the study scheme below). During the purposeful method, the time to results will not be included in the analysis.

Secondary endpoint:

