Once all the predefined range groups are covered, the study will be completed and the results will be analyzed.

Statistical considerations:

Passing Bablok regression analyses will be performed for each measurand between:

- (1) The mean value given by OLO for the finger prick samples and the value given by OLO for the venous sample.

- (2) The value given by OLO for the venous sample and the value given by Beckman Coulter DxH800 for the venous sample.

Measurands invalidated by either OLO or Beckman Coulter DxH800 will be removed from all analyses.

The time to result will be compared between the time of first available finger prick results (from the scan on OLO) and the time of available venous results (from the routine scan on Beckman Coulter).

After study completion, medical records of the enrolled patients will be reviewed to evaluate whether the same clinical decision would have been taken when based on OLO results.

Environmental requirements:

- OLO should be placed on a stable bench (shared with no vibrating equipment) with enough space for the device and an adjacent surface for sample preparation. OLO's physical measurements are: 25.7X32.6X28.7 cm, 10 kg.
- Power supply - OLO is provided with a power supply unit which needs to be connected to a standard grounded power socket.
- Internet connectivity - not mandatory for operation but preferable for remote support and monitoring. LAN connectivity is preferable. Sight can provide 3G/4G dongle for cellular connectivity. It would be best to contact an IT person directly to understand whether there are special compliance requirements when connecting OLO to the local network/internet.
- Each blood tube should be kept at room temperature of 18°C-26°C throughout the day until the last scan is completed. The OLO operating temperature range is 18°C-30°C, relative humidity range is 20%-80%.
- The reference device must be calibrated and approved for use according to the lab standard operating procedures during the entire performance evaluation study. If any calibration process is performed during the study, Sight should be informed, preferably in advance, to be able to take the steps required to avoid interference with the method comparison (such as the removal of the samples scanned before/after the calibration).
- Results from the OLO can be exported as a CSV file through a USB drive and sent via email.

Sharing of results:

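### For purposefully sampled patients, the decision review can set later OLO values against a decision that most naturally rests on an earlier, selecting CBC; the comparison should use the paired DxH800 value from the same study collection

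*Protocol*

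**What the plan says.** **Initial phase** (Protocol, Phlebotomy and Scanning Flow). The study tube is drawn at the routine phlebotomy: "During the routine blood collection, an additional venous sample will be collected in K₃EDTA tube as part of the study". The other tube is the routine one: "The second tube will be sent to the lab to be scanned on Beckman Coulter DxH800, as part of the routine procedure". OLO and DxH800 venous values thus share one draw.

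**Purposeful phase** (Protocol, Primary endpoint, Purposeful Sampling Method). Selection uses a result already in hand: "A sample will be enrolled according to the result received from the routine CBC test from the same day (on Beckman Coulter DxH800"). Collection follows: "Once enrolled in the study, the samples collection and scanning will be performed in the same order as in the initial phase". One analysis is withdrawn for this phase: "During the purposeful method, the time to results will not be included in the analysis".

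**Decision review** (Protocol, Statistical considerations). After the study ends, "medical records of the enrolled patients will be reviewed to evaluate whether the same clinical decision would have been taken when based on OLO results". The text makes no distinction by phase and names no index CBC.

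**Timing rules** (Protocol, Study Requirements). "All four scans will be performed within no more than 2 hours", and "All scans should be performed within 8 hours from phlebotomy". Neither rule mentions the interval between the enrolling CBC and the study collection.

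**The concern.** The Hypothesis section expects treatment decisions to stay the same when they are based on OLO. A fair test needs both analyzers to see the same blood, or at least blood taken together. The initial phase provides this. The purposeful phase, followed as written, may not: the patient is picked because a routine count was low, that count is already available to the clinic, and OLO is measured afterwards.

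A discordant decision then has several possible explanations, and the review as described cannot separate them. Agreement is also harder to interpret. The problem falls on the low-count ranges that purposeful sampling exists to fill. The Protocol recognises that this phase is unsuitable for one timing-dependent analysis (time to result) but does not consider the other.

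**Working it through.** The Protocol gives no figure for this point, so there is none to reproduce. The check is one of sequence, followed by the possible size.

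**1. Order of events**

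| Step | Initial phase | Purposeful phase |
|---|---|---|
| 1 | Consent and rest of at least 15 minutes | Routine draw |
| 2 | One phlebotomy: routine tube and study tube | Routine DxH800 result received |
| 3 | Two finger pricks on OLO, then the study tube on OLO; routine tube to the DxH800 | Enrolment on that result |
| 4 | Record review after completion | Study collection: finger pricks, study tube and, if the flow is repeated in full, a second DxH800 tube |
| 5 | – | Record review after completion |

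In the initial phase the decision-driving CBC and the OLO venous value come from the same draw. In the purposeful phase the CBC known first belongs to step 1 and the OLO values to step 4.

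**2. Limit on the gap.** If the fourth scan under the 2-hour rule is a new DxH800 scan, the gap back to the enrolling CBC is limited only by the same-day condition. If the fourth scan is the enrolling scan itself, scan times are close, but treatment in between is still not addressed. The 8-hour rule does not say which phlebotomy it counts from in this phase.

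**3. Direction of the selection effect.** Write the enrolling value as x1, the later value as x2, the mean in the patients screened as μ, and the same-day correlation between repeat values as ρ. With equal variances and a linear relation, E(x2 | x1) = μ + ρ(x1 − μ), so the expected shift is (1 − ρ)(μ − x1). For x1 below μ and ρ below 1 this is positive: later values move upward on average, even with no treatment and a perfect analyzer. The documents give neither ρ nor μ, so only the sign can be stated. If ρ is close to 1, the shift is small.

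**4. Share affected.** About 30 abnormal samples are planned out of about 50. The purposeful share is not stated. Assumed range: 0 (phase not needed) to 30/50 = 60% (every abnormal sample obtained this way).

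**5. Weight of one case.** Table 1 asks for 2 to 7 pairs per range. If decisions were read by range, which the Protocol does not specify, one misattributed discordance would be 1/2 = 50% of the smallest cell and 1/7 = 14% of the largest. Over all 50 samples it would be 1/50 = 2%.

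**The case against.** **No index CBC is named.** The review asks whether the same decision would have been taken on OLO results. It does not say that OLO is scored against the decision made on the enrolling CBC, and a repeated flow would place a second DxH800 result in the record. This stands: the earlier-CBC comparator is the natural reading, not a stated rule. It does not remove the problem, because nothing directs the review to the paired value.

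**The venous draw is uncertain.** The study scheme is not visible in the text available, and the Exclusion Criteria mention picking specimens from tube racks, which could mean that an already drawn tube is used. The OLO venous value might then share the routine draw. This also stands, but the finger pricks, whose accuracy the study sets out to establish, would still be later.

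**Treatment between the draws is assumed.** A reader might infer that a transfusion or infusion does intervene. For example, a platelet rise of 10 to 30 x10³/µL would move a patient enrolled at 15 to between 25 and 45, one or two Table 1 ranges higher. The documents do not support this. They mention no transfusion or infusion and give no such rise, and Table 1 sets sampling quotas rather than decision thresholds. Treatment is a possibility that the plan leaves open, no more.

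**This belongs in an analysis plan.** An analysis plan could choose the comparator. However, the worksheet time points listed in the Protocol include no treatment given before the study collection, and they do not identify the enrolling draw. Medical records may supply these, but the plan does not ask for them.

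**Scope is narrow.** The phase is conditional and the review is one sentence in what the Protocol calls an early comparison study. This is fair, and it limits the weight of the point.

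**Conclusion.** The point holds as a sequence problem confined to the decision comparison in the purposeful phase. As written, OLO values collected after enrolment (certainly the finger pricks, on the plain reading also the venous tube) may be compared with a decision resting on an earlier CBC that was itself used to select the patient. Elapsed time, regression to the mean and any intervening treatment are then mixed with the analyzer effect.

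The conclusion rests on one inference, that the recorded decision follows the routine CBC known before enrolment. The affected share is an assumption, and the size of any shift in counts cannot be derived from the documents.

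A reader might go further and infer that the Passing-Bablok regressions are compromised as well. They are not, provided that the paired DxH800 value comes from the study collection; the Protocol should say so. The change is worth making because it is cheap and bears directly on a stated hypothesis.

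**What to change.** 1. In Statistical considerations, state that for purposeful-phase patients the decision comparison uses the OLO value and the DxH800 value from the same study collection, judged in the same way, and not the decision recorded from the enrolling CBC. Alternatively, report the record-based comparison for the initial phase only.
2. State that the DxH800 value used in the Passing-Bablok analysis for these patients comes from the study collection.
3. Add to the worksheet the time of the enrolling draw and any treatment given between it and the study collection. Report the decision comparison with and without the treated patients.
4. Do not restrict enrolment on this account: exclusions could cost scarce low-count patients.

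Cost: a few Protocol sentences and one worksheet entry, with no change to care. The real loss is that for these patients the decision is inferred from paired values instead of being one actually taken and recorded.

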המרכז הרפואי תל-אביב
ע"ש סוראסקי
רפואה מובילה ואנושית

Proposed Study Title

Study Title

Performance Evaluation Protocol for Sight Diagnostics' OLO CBC Analyzer by Ichilov oncology daily care center.

Contact Information

Name

[name]

Job Title

VP R&D

Institution

Sight Diagnostics

Address 1

[name]

Address 2

City, State, Zip

Tel Aviv

Country

Israel

Phone/Fax

E-mail	[contact]
--------	--------------------

Study Information

Tumor Type	N/A				
Areas of Interest	N/A				
# of Patients	50	Study Duration (Months)	1	Number of Sites	1
Site Names	Sight Diagnostics				

Hypothesis / Overall Objectives

Background:

The Sight OLO is a quantitative multi-parameter automated hematology analyzer intended for in vitro diagnostic use in screening capillary or venous whole blood samples collected in K₂EDTA blood collection tubes, or fingertip samples collected using the Sight OLO test kit microcapillary tubes. When used with the Sight OLO cartridge, the Sight OLO enumerates the following CBC parameters in whole blood: WBC, RBC, HGB, HCT, MCV, MCH, MCHC, RDW, PLT, NEUT%/#, LYMPH %/#, MONO %/#, EOS%/#, and BASO%/#.

The Sight OLO is indicated for use in point of care and clinical laboratories to identify and classify one or more of the formed elements of blood in children 3 months and above, adolescents and adults. In case a different intended use is required by the evaluating site, Sight should be informed in advance.

As there are great benefits in performing CBC tests from fingertip in oncologic patients, this study aims to establish OLO’s performance accuracy of CBC results for finger prick samples across the OLO reportable range, and particularly around relevant medical decision points. Additionally, the study will evaluate OLO’s compatibility to Ichilov oncology daily care center, while focusing on its effect of workflow and turnaround time.

Hypothesis:

The results of this study are expected to show good performance of OLO and its equivalence to the site's standard hematology system - Beckman Coulter DxH800 analyzer - in samples spanned over a wide clinical measuring range and covering medical decision points for WBC, HGB, PLT, and NEUT#. The medical decisions taken for treating chemotherapy patients at the oncology center are expected to remain equal when based on the results given by Sight OLO.

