- Given this is an early comparison study, results will be shared openly across both parties.
- CSV files with the results of OLO and de-identified PDF files with the results of the reference device should be shared regularly by the study coordinator.
- Study worksheets and enrollment forms will be delivered once completely filled.

Study Population

Brief description, setting and key inclusion/exclusion criteria

Inclusion Criteria:

Blood samples will be collected from oncologic patients older than 18 years old arriving at the oncologic daily care center of Ichilov hospital.

The sampling method will initially be randomized, though will aim to include both normal and abnormal ranges of blood counts (according to Beckman Coulter DxH800 as the reference analyzer), while covering wide analytical ranges with balanced distributions, focusing on values around medical decision points. Approximately 30 abnormal samples will be collected, with the ranges to cover specified in table 1 below. Note that a single sample can cover multiple ranges for different parameters. Additionally, approximately 20 normal samples will be collected, while for the purpose of this protocol, normal is defined as samples with values above the ranges specified in table 1 for all parameters (PLT>100X10³/μL, HGB>12.0g/dL, WBC>4.0X10³/μL, NEUT#>2.0X10³/μL), and with no flags on the site reference analyzer.

Table 1 - abnormal ranges

[figure not shown]
	Range	# of paired samples
PLT	<100X10 ³ /μL and >50X10 ³ /μL	2
	<50X10 ³ /μL and >30X10 ³ /μL	4
	<30X10 ³ /μL and >18X10 ³ /μL	4
	<18X10 ³ /μL	4
HGB	<12.0g/dL and >10.0g/dL	4
	<10.0g/dL and >4.0g/dL	4
WBC	<4.0X10 ³ /μL and >2.0X10 ³ /μL	2
	<2.0X10 ³ /μL	7
NEUT#	<2.0X10 ³ /μL and >1.0X10 ³ /μL	3
	<1.0X10 ³ /μL and >0.5X10 ³ /μL	3
	<0.5X10 ³ /μL	2

Exclusion Criteria:

- Visibly hemolyzed specimens (sample plasma should be checked for hemolysis by technician while selection of specimen from tube racks).
- Visibly clotted specimens (Reasonable to assume that samples processed with clinical reported results are not clotted).
- A sample that is not successfully scanned on OLO within 3 attempts (e.g. rejected due to irregular cell morphology, or microscopically visible hemolysis).

Study Schema

Please insert a graphic study schema or visual representation of trial design

Protocol revision signatures: This study protocol has been reviewed by Sight's key personnel with their signature approval for its use.

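### The one pooled Passing-Bablok line per measurand dilutes a bias confined to the lowest ranges; range-specific paired differences should be added

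*Protocol*

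**What the plan says.** The Background section of the protocol states the aim as accuracy of finger-prick results "across the OLO reportable range, and particularly around relevant medical decision points". The Hypothesis section expects equivalence to the DxH800 in samples covering decision points for WBC, HGB, PLT and NEUT#.

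Sampling follows that aim. Overall, "approximately 50 whole blood samples will be collected from patients at the oncology daily care center". Under Inclusion Criteria, "Approximately 30 abnormal samples will be collected, with the ranges to cover specified in table 1 below", and "approximately 20 normal samples will be collected" with values above the Table 1 ranges on all four parameters. Table 1 sets targets in its column for the number "of paired samples" per range, with the remark: "Note that a single sample can cover multiple ranges for different parameters". The sampling should aim at "covering wide analytical ranges with balanced distributions, focusing on values around medical decision points". Sampling ends once every range is filled.

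Under Statistical considerations, "Passing Bablok regression analyses will be performed for each measurand between" two pairs of results: (1) the mean finger-prick value and the venous value, both on OLO; (2) the venous value on OLO and on the DxH800. The same section plans a time-to-result comparison and a review of medical records to see whether clinical decisions would have been the same on OLO results. No stated accuracy analysis uses the Table 1 ranges.

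**The concern.** The sampling is built around low ranges, and the stated analysis then pools those samples with a larger number of higher ones. The Passing-Bablok slope is a median of pairwise slopes, so it is designed to resist a discordant minority. If OLO, or the finger-prick specimen, is off only at low counts, the low samples are that minority. The line then moves only part of the way towards them, and its value at the decision point understates the bias there.

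At stake is the statement that the study most wants to make: that results agree near the values on which treatment decisions rest. A pooled line close to identity is weak evidence for that when few low samples contribute to it. Both comparisons are affected in the same way.

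**Working it through.** **Plan's own count.** 30 abnormal + 20 normal = 50, as stated. The Table 1 targets per measurand are:

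- PLT 2 + 4 + 4 + 4 = 14
- HGB 4 + 4 = 8
- WBC 2 + 7 = 9
- NEUT# 3 + 3 + 2 = 8

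These are 14 + 8 + 9 + 8 = 39 places. They fit into 30 samples if overlaps save 39 - 30 = 9 places, which the protocol allows. The just-met case is therefore compatible with the plan.

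**Lowest ranges at those targets.** PLT below 50: 4 + 4 + 4 = 12. HGB below 10.0: 4. WBC below 2.0: 7. NEUT# below 1.0: 3 + 2 = 5.

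**Which pairs set the slope.** With n = 50 there are 50 × 49 / 2 = 1,225 pairwise slopes. With m samples above the abnormal limit and k = 50 - m below it, the shares are m(m-1)/2 and k(k-1)/2 over 1,225.

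| Measurand | Above / below limit | Both above | Both below |
|---|---|---|---|
| PLT | 36 / 14 | 630 = 51% | 91 = 7% |
| HGB | 42 / 8 | 861 = 70% | 28 = 2% |
| WBC | 41 / 9 | 820 = 67% | 36 = 3% |
| NEUT# | 42 / 8 | 861 = 70% | 28 = 2% |

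**Simulation at the just-met targets.** Passing-Bablok with shifted-median slope and rank-based 95% CI, n = 50, 1,500-2,000 studies per scenario. The protocol gives no error or bias sizes, so these are assumptions:

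- values uniform within each Table 1 range; the rest uniform above it (PLT 100-400, HGB 12-16, WBC 4-11, NEUT# 2-8);
- equal error on both sides, CV 1-2% for HGB and 2-6% for the others, plus a small constant SD;
- a constant step bias in the lowest range and none above it.

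Missed means that the slope CI contains 1 and the intercept CI contains 0. Ranges span three error levels.

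| Assumed bias | Line shows | Share shown | Missed by line | Found by low-range paired difference |
|---|---|---|---|---|
| HGB +1.0 below 10 | +0.16 to +0.33 (at 9-10) | 16-33% | 64-73% | 89-99% |
| NEUT# +0.3 below 1.0 | +0.09 to +0.14 (at 0.5) | 30-47% | 44-71% | 89-100% |
| WBC +0.4 below 2.0 | about +0.2 (at 2.0) | about 50% | 18-53% | about 100% |
| PLT +5 below 50 | about +4 (at 18) | about 80% | 8-63% | 77-100% |

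With no bias, the line flags 5-9% and the paired difference about 5%. A repeat with 1,000 studies per scenario gave +0.18 to +0.28 for HGB, +0.09 to +0.14 for NEUT#, +0.19 to +0.24 for WBC (48-60% of +0.4) and +4.0 to +4.4 for PLT.

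Other assumed biases and error levels also gave shrinkage in every scenario. If the PLT bias is confined to values below 30 (8 samples), 45-70% of it is shown.

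**More low samples.**

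- NEUT#, 8 or 12 samples below 1.0: the +0.3 bias is seen in 83% or 100% of studies, but the line shows +0.18 or +0.23 (60% or 77%).
- HGB, 20 samples below 12 of which 10 are below 10: the +1.0 bias is seen in about 98%, with about +0.4 shown.
- All 30 abnormal samples low on the same measurand: no run missed the bias, and 44-91% of it was shown.

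**The case against.** Several objections have force.

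- *Range-specific estimates can be left to a statistical analysis plan.* One may exist and may add them. But the protocol does name its accuracy method, and that method, followed as written, understates bias in the ranges the study is designed to fill. The mismatch lies in stated text.
- *The record review covers decision points.* It bears directly on whether decisions would change, and it must be counted. It does not estimate bias, so it complements an accuracy analysis and does not replace one.
- *Table 1 gives targets, not achieved counts.* This stands. For HGB to stay at 8, 30 - 8 = 22 of the abnormal samples would need HGB above 12.0. Easier ranges may overfill, and then most misses vanish. Shrinkage remains.
- *The bias model favours the paired difference.* This also stands. If the bias varies between patients with SD 0.5 g/dL (assumed), detection from 4 HGB samples falls to 65-71%; with SD 0.3 for NEUT#, to 35-42%. A signed-rank test cannot reach two-sided 0.05 there: the smallest p is 2 × (1/2)^4 = 0.125 with 4 samples and 2 × (1/2)^5 = 0.0625 with 5.

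A reader might also infer more than the protocol supports. No rule in it treats a near-identity line as proof of equivalence, and it calls itself an early comparison study. Resistance of the median slope to a minority does not mean that low samples are ignored, as PLT shows. The phrase on balanced distributions is an aim, so its tension with the targets is minor.

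**Conclusion.** The point holds as a mismatch between aim and stated analysis. At just-met targets, the pooled line shows roughly 20-30% of a step bias for HGB below 10, 30-50% for NEUT# below 1.0 and 50-60% for WBC below 2.0. It misses the bias in a substantial share of studies, about two thirds for HGB. For a PLT step below 50 the shrinkage is small.

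The dilution is robust across the scenarios tried. The miss rates are not: they depend on the minimum counts, the assumed error levels and a constant step bias, none of which the protocol fixes. It would be too strong to say that low-range bias will usually go unseen on all four measurands. This is a worthwhile improvement, not a condition for starting.

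**What to change.** Keep both Passing-Bablok regressions. Add to Statistical considerations, for PLT, HGB, WBC and NEUT# and for each of the two comparisons:

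1. the mean paired difference with 95% CI within PLT below 50, HGB below 10.0, WBC below 2.0 and NEUT# below 1.0;
2. a cross-table of Table 1 category by the two methods.

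Assign range by the DxH800 value, as Inclusion Criteria does. In comparison (2) the DxH800 is also one of the two results compared, so repeat the estimate with range set by the average of the two analyzers. Use that only as a sensitivity check, because the average can move biased samples out of the range: DxH800 9.6 and OLO 10.6 average 10.1.

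Base statements about accuracy at decision points on these estimates and not on the pooled line alone. Report results from 4-5 samples (HGB below 10, NEUT# below 1.0) as estimates with their intervals, not as proof of equivalence. If convenient, align the wording on balanced distributions with Table 1.

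The cost is a short addition to the text, with no extra samples or procedures. The downside is wide intervals, so the claim at low values becomes less favourable; narrower ones would need more low samples.

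### No planned accuracy analysis compares a finger-prick result with the DxH800, and the only one with finger-prick values averages two pricks

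*Protocol*

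**What the plan says.** The Background under Hypothesis / Overall Objectives states the aim as "performance accuracy of CBC results for finger prick samples across the OLO reportable range, and particularly around relevant medical decision points". The Hypothesis expects equivalence of OLO to the Beckman Coulter DxH800 "in samples spanned over a wide clinical measuring range and covering medical decision points for WBC, HGB, PLT, and NEUT"#, and expects treatment decisions to stay the same on OLO results.

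Study design sets up two parts: "A matrix study will compare a capillary sample collected via finger prick with a venous sample", both on OLO, and "A method comparison study will compare Sight OLO to Beckman Coulter DxH800 using a venous sample collected into a blood tube".

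Statistical considerations turns these into two Passing-Bablok regressions per measurand. Regression 1 stays within OLO and pairs "The mean value given by OLO for the finger prick samples and the value given by OLO for the venous sample". Regression 2 drops the finger prick altogether and brings in the reference analyser, pairing "The value given by OLO for the venous sample and the value given by Beckman Coulter DxH800 for the venous sample".

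The same section takes time to result from the first available finger-prick result. It also plans a later review of medical records to "evaluate whether the same clinical decision would have been taken when based on OLO results".

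Each included patient supplies two finger-prick OLO values, one venous OLO value and one DxH800 value. Study Requirements adds: "If less than 2 finger prick scans are completed successfully, the sample should be excluded from the study".

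**The concern.** The question the study sets itself is whether a finger-prick result can stand in for the laboratory result when it lies near a decision point. Followed exactly, the plan reaches the DxH800 from the finger prick only through an intermediate, the venous OLO value, and it averages two pricks on the way. The result credited for speed, the first prick, is therefore never the result tested for accuracy.

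Both regressions could look satisfactory while a single prick falls on the other side of a cut-off from the DxH800 more often than the venous OLO value does. Whether that happens depends on finger-prick imprecision, which the protocol does not give and the two regressions do not report. The record review is the one analysis that could show it directly. It refers only to OLO results, so any of the three OLO values could be used, and the choice could be made after the results are known.

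**Working it through.** **Pairings.** This part needs no assumption.

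| Analysis | Finger-prick value | Compared with |
|---|---|---|
| Regression 1 | mean of two | OLO venous |
| Regression 2 | none | DxH800 venous (against OLO venous) |
| Time to result | first prick (time only) | DxH800 (time only) |
| Decision review | not stated | decision actually taken |

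**Average bias is bridged.** With an assumed matrix factor of 1.04 and analyser factor of 1.05, the true slope of finger prick on DxH800 is 1.04 × 1.05 = 1.092. In 2,000 simulated studies of 50 patients per setting (values log-uniform from 15 to 300, between-prick CV 3–15%, shared capillary CV 0 or 5%), the chained slope averaged 1.092–1.104 and the direct one-prick slope 1.092–1.116. The split design loses little here.

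**Scatter is not bridged.** Let b be the between-prick CV, s the capillary error shared by both pricks, v the OLO venous CV and d the DxH800 CV. The variances of the differences are:

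- regression 1: s² + b²/2 + v²
- regression 2: v² + d²
- one prick against DxH800: s² + b² + d²

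The third equals the sum of the first two plus b²/2 − 2v². Neither regression reports b or v, so the third cannot be worked out from their separate outputs. Averaging also reduces the between-prick SD by a factor of 1/√2 = 0.71.

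**Disagreement at a cut-off.** All CVs are assumptions: v = d = 3%, b = 3–15%, s = 0 or 5%, no bias. True values are uniform within ±20% of a cut-off, with 2,000,000 draws per setting. The table gives the percentage on the opposite side from the DxH800. The last column is the percentage of patients whose three OLO values are not all on the same side.

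| b, s (%) | One prick | Mean of two | OLO venous | Three OLO values mixed |
|---|---|---|---|---|
| 3, 0 | 8.5 | 7.4 | 8.5 | 12.8 |
| 3, 5 | 13.2 | 12.4 | 8.5 | 17.4 |
| 5, 0 | 11.7 | 9.2 | 8.5 | 18.8 |
| 5, 5 | 15.4 | 13.7 | 8.5 | 22.4 |
| 8, 0 | 17.0 | 12.8 | 8.5 | 28.3 |
| 15, 5 | 28.1 | 23.1 | 8.5 | 45.5 |

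A hand check, good while errors are small against the window: the rate is about √(2/π) × SD of the difference ÷ 40. For b = s = 5, the SD is √(25 + 25 + 9) = 7.7%, and 0.798 × 7.7 ÷ 40 = 15.4%. For OLO venous, the SD is √(9 + 9) = 4.24%, giving 8.5%.

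**Further from the cut-offs the rates fall.**

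| Spread of true values | One prick, b = 3 | b = 5 | b = 8–15 | OLO venous |
|---|---|---|---|---|
| Within ±30% | 5.7–8.8 | 7.8–10.3 | 11.5–20.9 | 5.7 |
| Log-uniform 15–300, platelet cut-offs 18, 30, 50, 100 | 4.5–7.0 | 6.2–8.2 | 9.1–17.2 | 4.5 |

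On the log-uniform spread the three OLO values are mixed in 6.8–9.3%, 10.0–12.0% and 15.2–28.4%.

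**What about 50 patients can show.**

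- Cut-off counts: Table 1 plans 2–7 samples per range. With no discordant sample the one-sided 95% upper bound is 1 − 0.05^(1/n): 78% for n = 2, 63% for 3, 53% for 4 and 35% for 7.
- Limits of agreement: each limit has a 95% half-width of t(0.975, 49) × √(1/50 + 1.96²/(2 × 49)) = 0.489 SD. If the SD is 7.7%, that is 0.489 × 7.7 = 3.8 percentage points.

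**The case against.** The strongest reply is that a matrix study plus a method comparison is a coherent design. It separates specimen effect from analyser effect, and the two steps together give the average bias. The sentence stating the finger-prick aim names no comparator; the DxH800 enters in the hypothesis about OLO in general. The protocol's intended use also covers venous samples. All of this is correct, and it is why both regressions should stay. It does not supply the total error of one prick, which is what accuracy near a decision point and unchanged decisions require.

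Second, the plan already contains capillary data, so the fair contrast for the averaging is one prick against the two-prick mean. Within ±20% of a cut-off that gap is about 1–2.5 percentage points at between-prick CVs of 3–5%, and 4–5 points in the 8% and 15% rows of the table. High imprecision would also be partly visible in regression 1: at b = 15, s = 5 its difference SD is √(25 + 112.5 + 9) = 12.1%, against √(25 + 225 + 9) = 16.1% for one prick against the DxH800. This stands, and it limits how far the largest rates could go unnoticed. It does not limit the low and middle range in the same way: at b = s = 5 the SDs are 6.8% and 7.7%, and nothing planned reports the latter.

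Third, no data are lost, and a statistical analysis plan could add analyses. That is true, but the protocol itself fixes the pairings and the averaging, so the point concerns what is stated rather than detail left for later. Finally, cut-off counts in ranges of 2–7 samples prove little. That also stands, and they should be labelled descriptive.

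**Conclusion.** The concern holds. As fixed, no accuracy analysis sets a finger-prick value against the DxH800 or uses a single prick, and the decision review leaves open which OLO value counts. That conclusion rests on the text alone.

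The size of the consequence rests on assumed CVs. It ranges from nothing (between-prick CV 3% with no shared capillary error, where one prick does as well as venous OLO at 8.5%) to about 28% disagreement near a cut-off at CV 15%. It is smaller when values are spread more widely. Average bias is not at risk. The study can run and its regressions remain valid, but they do not directly support the finger-prick claim. This should be fixed.

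**What to change.** In Statistical considerations, keep regressions 1 and 2, including the two-prick mean, and add:

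- For each measurand, the first valid finger-prick OLO result against the DxH800 result: Passing-Bablok regression, bias and limits of agreement.
- Descriptive agreement counts at the Table 1 cut-offs, with exact intervals.
- Between-prick repeatability from the two pricks.
- A statement that the decision review uses that same first valid finger-prick result, with the venous OLO result as supportive.

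The cost is wording and extra analysis. Study Requirements already demands two valid finger-prick scans and valid venous scans for every included patient, so no further blood is needed; measurands invalidated by either analyser stay excluded. The reported scatter will be wider than for the two-prick mean. The cut-off counts will not establish agreement by themselves, so the limits of agreement should carry most of the weight.

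Suggested wording: The first valid finger-prick OLO result will be compared with the DxH800 result for each measurand by Passing-Bablok regression and limits of agreement. The same finger-prick result will be used in the review of clinical decisions.
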